6.3.3. Laboratory Tests

A repeat urine pregnancy test will be performed at discharge, i.e. between D13 and D18.

Blood haematology and biochemistry assessments will be repeated on D5, D8 and D11 (EOT visit). Safety biochemistry and haematology assessments will be performed 9 weeks after intake of the first dose on D1, only in patients who reach this visit from mid-December 2014 onwards. Blood samples will be analysed in the laboratory in each centre using standard equipment specifically provided for the study by the Sponsor. Whenever possible, the samples should be collected from patients in the fasting state.

Parasitology testing requires 5 mL of whole venous blood or 4 mL of CSF. The blood sample should be analysed on an mAECT column within 30 minutes after collection. The CSF sample should be examined after MSC within 15 minutes after collection. The WBC in the CSF sample should be performed within 15 minutes after collection. It is necessary to collect 5 mL of CSF to perform the two tests.

Full haematological and biochemistry analyses require at least 0.5 mL of capillary or venous blood. Capillary blood collection considerably reduces the total quantity of blood collected as compared to classical techniques. However, because it is not always feasible, collection of venous blood is permitted. Each sample corresponds to 2 mL per tube, one tube containing EDTA for Haematology and one tube containing heparin lithium for Biochemistry.

The urine analyses performed at screening, at the baseline assessment and at the EOT visit, as well as on D18 and at 3 months for female patients, require only a few millilitres (5-10 mL).

During hospitalisation, additional safety assessments such as haematology, biochemistry or urine tests may be performed at the discretion of the Investigator in order to monitor for abnormalities.

The volume and the number of samples required for each patient are presented by visit in Appendix 3 – Laboratory Assessments (p 96).

6.3.4. PK Assessments

All patients in the fexinidazole group, included in the first 6 investigational centres opened, will undergo PK assessments.

The sampling procedure and assay method will be described in the corresponding laboratory manual.

 Approximately 300 µL of whole blood will be collected on filter paper by finger-prick for DBS testing at each of the following timepoints:

Ideal timepoint for sampling	Leeway
D8 3 hours 15 minutes after intake of the IP	± 5 minutes
D9 3 hours after intake of the IP	± 5 minutes
D10 3 hours and 7 hours and 15 minutes after intake of the IP	± 15 minutes
D11 24 hours after the last intake of the IP	± 1 hour
D12 48 hours after the last intake of the IP	± 1 hour

 The timing of sample collection was optimised with WinPOPT® software using the parameters of population PK modelling pooled from the DNDiFEX001 and DNDiFEX002 studies. The timepoints for sampling were chosen in order to obtain the best predictions of pre-dose M2 concentrations. Lumber puncture will be performed on D11 24 hours after the last intake of the IP, and the CSF sample will be analysed using dried spot sampling. Dried spot sampling of CSF will be performed on all patients up to the end of July 2013.

The CSF dried spot samples will be stored under the same conditions (see laboratory manual).

6.4. Assessments at Follow-up Visits

Should a patient move residence during the course of the study, the follow-up visits can be performed at Kinshasa by the coordination team (PNLTHA and INRB) or at the new location by the site investigator together with his/her required staff. Related documentation will be forwarded to the initial clinical site who will enter the data into the CRF".

6.4.1. At the Additional Visit 9 Weeks after D1

- Haematology: haemoglobin, WBC count and differential, platelet count
- Biochemistry
- Physical examination including vital signs
- Neurological examination

6.4.2. At the 3-month Follow-up Visit

- Physical examination, HAT symptoms since discharge, neurological assessment including signs and symptoms of HAT
- Testing for *T.b. gambiense* in blood and lymph for diagnosis of potential relapse
- CSF sampling and analysis (MSC with INRB kits) only if symptoms suggesting disease progression are present
- Urine pregnancy test in female patients of child-bearing potential to investigate possible exposure *in utero* (see Section 6.5.8. Exposure *in utero*; p 55)
- Additional safety assessments such as ECG, haematology, biochemistry or urine tests may be performed at the discretion of the Investigator. An ECG recording may be required at the M3 visit if the cardiologist issued an alert at the EOH visit.

6.4.3. At the 6, 12 and 18-month Follow-up Visits

- Physical examination, HAT symptoms since the previous visit, neurological assessment including signs and symptoms of HAT
- Testing for *T.b. gambiense* in blood and lymph for diagnosis of potential relapse

- CSF sampling to test for potential relapse, with WBC count and testing for trypanosomes (Fuchs-Rosenthal/Fast Read 102® counting chamber, MSC with INRB kits)
- Additional safety assessments such as ECG, haematology, biochemistry or urine tests may be performed at the discretion of the Investigator.

6.4.4. At the 24-month Follow-up Visit

- Physical examination, HAT symptoms since hospital discharge, neurological assessment including signs and symptoms of HAT
- Testing for *T.b. gambiense* if relapse is suspected or if required according to current local standard of care.
- Additional safety assessments such as ECG, haematology, biochemistry or urine tests may be performed at the discretion of the Investigator

6.4.5. At Unscheduled Visits

If a relapse is suspected on the basis of physical examination findings or CSF WBC count, at any visit, the patient must attend a return visit within 1 to 3 months, at the discretion of the Investigator.

The patient must also return to the investigational centre if s/he does not feel well, even if there is no apparent relationship with treatment and/or HAT.

The following assessments will be performed:

- Physical examination, HAT symptoms since the last visit, neurological assessment, including signs and symptoms of HAT
- Investigation of any concomitant condition that may have led to the visit
- Testing for *T.b. gambiense* in blood and lymph, if indicated
- CSF sampling (Fuchs-Rosenthal/Fast Read 102[®] counting chamber, MSC with INRB kits): only if symptoms suggesting disease progression are present
- Additional safety assessments such as ECG, haematology, biochemistry or urine tests may be performed at the discretion of the Investigator.

6.5. Safety Assessments, Definitions and Reporting of Adverse Events

The safety and tolerability of treatment will be assessed through routine monitoring of adverse events (AEs). During the observation period, the study personnel will collect AEs every day.

The **observation period** will extend from the start of treatment (D1) to hospital discharge, planned on D18, but potentially taking place as early as D13 if the patient's status allows it.

In addition, patients will be advised to return to the hospital/investigational centre at any time during the follow-up period if they experience any AEs, in order to undergo additional safety assessments.

Safety data will be reviewed at each meeting of the DSMB/ISC.

Safety endpoints will be classified as follows:

- Occurrence of any adverse events ≥ grade 3, including laboratory abnormalities, during the observation period. Adverse events will be graded according to the NCI CTCAE, Version 4.03 (38)
- Occurrence of any adverse events, including laboratory abnormalities, (all grades combined) during the observation period
- Occurrence of any treatment-related adverse events, including laboratory abnormalities, (≥ grade 3 and all grades combined) during the observation period
- Occurrence of any serious adverse events, including laboratory abnormalities, between the first treatment intake and the end of the followup period (18 months)
- Occurrence of any serious adverse events, including laboratory abnormalities, between the first treatment intake and the end of the additional follow-up period (24 months).

6.5.1. Definition of AE

An AE is defined as any untoward and unintended medical occurrence (sign, symptom or disease), including a clinically significant abnormal laboratory or ECG finding, or worsening of any pre-existing condition during the study, whether or not it is considered to be study related.

Any abnormal laboratory result on haematology, biochemistry or urine analysis will be reported as an AE if it occurs or worsens after the start of the study treatment, and if the CTCAE grade is > 1, unless it is associated with a previously reported clinical event.

The Investigator or appropriate study personnel will examine any patient who experiences an AE as soon as possible. The Investigator will do whatever is medically necessary for the patient's safety and well-being. The patient will remain under observation as long as s/he is receiving study treatment and up to the last day of the observation period (between D13 and D18), or longer if medically indicated in the opinion of the Investigator. All AEs observed or reported following administration of the study treatment will be followed until resolved or until the Investigator considers them to be "chronic" or "stable".

All identified AEs will be recorded in the appropriate AE section of the e-CRF using concise medical terminology, and avoiding vague, ambiguous or colloquial language. SAEs will be reported by telephone, Short Message Service (SMS) or email to Swiss TPH (see Section 6.5.5 Requirements for AE Reporting; p 54).

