6.5.6. Grading of AE Severity

The severity of the AE must be graded according to NCI CTCAE, version 4.03 (38). For some biological parameters, the NCI CTCAE criteria have been adapted (i.e. hemoglobin, leucocytes, sodium, calcium, creatinine). If the AE is not described in the CTCAE, version 4.03, the Investigator will use the terms "mild", "moderate" or "severe" to describe the maximum severity, as defined below:

Mild	does not interfere with the patient's usual activities
Moderate	interferes to some extent with the patient's usual activities
Severe	significantly interferes with the patient's usual activities

The information concerning AE grading must be recorded in the AE section of the e-CRF.

It is important to distinguish between the severity and the seriousness of AEs: a severe AE is not necessarily an SAE.

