6.5.9. Follow-up on AEs

All AEs must be followed until resolution, or until the Investigator considers them to be "chronic" or "stable", or until the patient's participation in the study ends, i.e. until the final report is completed for the study in which the patient was participating.

If the AE is a laboratory abnormality with a toxicity grade \geq 3, the test must be repeated 2 to 4 days later, and then at regular intervals until the parameter reaches toxicity grade \leq 1, or until it returns to the baseline level (see Baseline Assessment).

In addition, all SAEs and all events that the Investigator (and the Coordinating Investigator or the monitor, as needed) considers as possibly related to the study treatment must continue to be followed even after the end of the patient's participation in the study. Such events should be followed until their resolution, or until the Investigator considers them as "chronic" or "stable." The resolution of such events must be documented in the e-CRF, and if they are SAEs, on an SAE follow-up form.

7. Study Duration

The enrolment period is expected to last 18-20 months (see Table 7 – Expected Enrolment Rate; p 104). The duration of treatment will be 10 days in both treatment groups.

Each patient's participation will last approximately 25 months and will include:

- pre-treatment period (pre-screening and screening, treatment of concurrent disease)
- treatment period of 10 days
- hospitalisation for 3 to 8 days after treatment
- out-patient follow-up for 18 months, until the TOC visit

• additional follow-up for 6 months, until M24

The total duration of the study, including the preparative phase, is expected to be 48 months.

8. Withdrawal Criteria

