8.2. Rules for Definitive Discontinuation of Treatment

The Investigator will discontinue the study treatment in the following cases:

- Severe skin reaction
- ALAT or ASAT exceeding 8 x ULN
- ALAT or ASAT exceeding 3 x ULN associated with total bilirubin > 2 x ULN
- ALAT or ASAT exceeding 3 x ULN accompanied by fatigue, nausea, vomiting, right upper quadrant pain or tenderness, fever, rash, and/or eosinophilia (>5%)
- pre-dose QTcF measurement ≥ 500 ms on D2, D3, D4 or D4H23, confirmed by a second ECG recorded after at least a 10-20 minute rest
- Any condition that, in the opinion of the Investigator, requires treatment discontinuation for medical reasons.

If a patient is withdrawn from the study before the end of treatment, the physician will make all necessary arrangements to ensure that s/he receives the appropriate treatment for the condition in question.

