9.9. Safety Analyses

All patients who received at least one dose of study treatment will be included in the safety analyses.

The percentage of patients with SAEs and/or AEs leading to treatment discontinuation will be presented for each treatment group and by system-organ class, using appropriate MedDRA preferred terms, according to the NCI CTCAE, version 4.03.

The percentage of patients with at least one AE will be described. Patients in whom an AE with the same preferred term occurred several times will be counted only once. If a patient experienced several AEs described using the same preferred term, the AE with the maximum severity will be used in the analysis. In addition, each SAE will be presented in a narrative describing all aspects of the medical event with a causality assessment.

AEs not leading to treatment discontinuation will be presented for each treatment group using the same classification as presented above.

The incidence of SAEs and AEs, along with the respective 95% confidence intervals will be presented for each treatment group, by category and by frequency. In other cases, only descriptive statistics will be presented.

Laboratory safety parameters, i.e. haematology and biochemistry, will also be presented for each treatment group, indicating the percentage of patients, the size of the increase in the value in relation to the ULN and baseline value, and changes in blood levels over time. Shift tables will be presented. A listing of patients with laboratory abnormalities will be provided.

ECG abnormalities will be presented for each treatment group and for each timepoint within each treatment group.

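### Section 6.5.1 can keep a grade 3-4 laboratory result out of the grade ≥ 3 adverse-event endpoints that section 6.5 says include it

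*Protocol*

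**What the plan says.** - **Reporting rule, protocol section 6.5.1.** A haematology, biochemistry or urine result that appears or worsens after treatment starts is reported as an AE "if the CTCAE grade is > 1, unless it is associated with a previously reported clinical event". The exemption covers every grade above 1.
- **General definition, same section.** The opening sentence defines an AE as "including a clinically significant abnormal laboratory or ECG finding, or worsening of any pre-existing condition during the study". It carries no exemption.
- **Endpoints, section 6.5.** One is "Occurrence of any adverse events ≥ grade 3, including laboratory abnormalities, during the observation period". Another is "Occurrence of any treatment-related adverse events, including laboratory abnormalities", for grade ≥ 3 and for all grades. Neither repeats the exemption. Section 2.2.2 lists the same families of endpoints and names laboratory abnormalities from grade 2 under the all-grade endpoint.
- **Grading, section 6.5.6.** "The severity of the AE must be graded according to NCI CTCAE, version 4.03". Nothing is said about a clinical event with a linked laboratory finding of a higher grade.
- **Analysis, section 9.9.** When a patient has several AEs with one preferred term, "the AE with the maximum severity will be used in the analysis". Laboratory values are summarised by arm as well, with shift tables and a patient listing.
- **Follow-up, section 6.5.9.** The repeat-test rule, which applies from grade 3, opens with "If the AE is a laboratory abnormality with a toxicity grade".

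**The concern.** The endpoint promises to count laboratory abnormalities of grade 3 or more. The reporting rule that feeds it lets some of them go unreported. Take a patient with grade 1 vomiting already on file and a later grade 3 ALAT that the investigator considers part of the same episode. Under 6.5.1 no separate AE is required, so the only recorded AE is grade 1 and the patient does not count in the grade ≥ 3 endpoint.

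The timing makes this a realistic path. Section 6.5 has AEs collected daily in hospital, while section 6.3.3 schedules post-baseline blood tests in hospital on D5, D8 and D11 only. A symptom may well be on file before the laboratory result exists. The judgement of association is made by investigators who know the treatment (section 5.7).

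What is at stake is an understated count in a declared safety endpoint. If linkage is judged more often in one arm than in the other, the comparison of that endpoint is also distorted.

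**Working it through.** The protocol states no figure for this point, so there is nothing to reproduce. The check has two parts.

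**1. Does any other rule bring the lost grade back?**

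- *Grading (6.5.6).* Each AE is graded as itself. No rule gives a clinical event the grade of a linked laboratory finding.
- *Maximum severity (9.9).* This works only within one preferred term. A vomiting term cannot take over the grade of an ALAT term.
- *Opening sentence of 6.5.1.* Read alone, it makes any clinically significant laboratory finding an AE. That conflicts with the exemption two sentences later, and the section does not say which prevails. Sites could follow either.
- *Laboratory tables (9.9).* They keep the values. However, causality under 6.5.7 is assessed for AEs, so an exempted result has no causality judgement of its own. The tables cannot rebuild the treatment-related grade ≥ 3 endpoint.

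A patient is therefore lost from the grade ≥ 3 endpoints only when all of the following hold: the clinical event was reported before the laboratory result; the result is judged associated with it; the clinical event is below grade 3; and the patient has no other AE of grade 3 or more.

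**2. How large could the loss be?** The inputs below are assumptions, not protocol figures:

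- L = true share of patients with a grade ≥ 3 laboratory abnormality and no clinical AE of grade ≥ 3, taken as equal in both arms
- s = share of these with an earlier reported clinical event below grade 3
- a = share of those judged associated

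Recorded rate = L × (1 − s × a).

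With equal linkage, L = 10%, s = 50% and a = 0.5, the rate is 0.10 × (1 − 0.25) = 7.5% in both arms. With the planned 260 and 130 patients (section 9.1), 26 × 0.25 = 6.5 and 13 × 0.25 = 3.25 patients would be missed. The difference between arms is zero.

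With unequal linkage, s = 80% in one arm and 40% in the other:

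| L | a | Higher-linkage arm | Lower-linkage arm | Spurious difference |
|---|---|---|---|---|
| 5% | 0.5 | 3.0% | 4.0% | −1 point |
| 5% | 1 | 1.0% | 3.0% | −2 points |
| 10% | 0.25 | 8.0% | 9.0% | −1 point |
| 10% | 0.5 | 6.0% | 8.0% | −2 points |
| 10% | 1 | 2.0% | 6.0% | −4 points |
| 20% | 0.5 | 12.0% | 16.0% | −4 points |
| 20% | 1 | 4.0% | 12.0% | −8 points |

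Example: 0.10 × (1 − 0.8 × 0.5) = 6.0% and 0.10 × (1 − 0.4 × 0.5) = 8.0%. With a = 0, that is, no exemption, the recorded rate equals L in both arms.

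**The case against.** The natural defence is that the clause is ordinary de-duplication: a laboratory result that belongs to a reported event should not be entered twice. That is probably the intent. The text does not confine the clause to that purpose, though, and does not say which grade the single entry takes.

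A second defence is that deriving laboratory components is work for the SAP, which is not at hand. The SAP may well derive them from laboratory values. It could not supply a causality judgement that was never collected, and the conflict between 6.5.1 and 6.5 is in the protocol itself.

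Several stronger readings are tempting and are not supported:

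- *That symptomatic grade 3-4 abnormalities drop out generally.* They do so only under the joint conditions set out above. An abnormality found before the symptom is reported still counts, and so does a patient whose clinical AE is itself grade 3 or more.
- *That the any-AE endpoint is understated.* It counts patients, and the linked clinical event already makes the patient count.
- *That a liver signal is lost.* The criterion in section 8.2 "ALAT or ASAT exceeding 3 x ULN accompanied by fatigue, nausea, vomiting" or the other listed signs rests on measured values and symptoms, not on an AE form. Section 6.5.2 makes raised ALAT/ASAT with raised bilirubin a serious AE, with no exemption.
- *That follow-up lapses.* Blood tests are scheduled for all patients, and 6.5.1 has every reported AE followed. Only the literal scope of the 6.5.9 repeat-test rule is unclear.
- *That the comparison is biased in favour of fexinidazole.* The protocol gives no comparative symptom rates. Section 1.7 describes gastrointestinal symptoms and one marked liver-enzyme rise with fexinidazole, but that rise came after 14 days at the highest dose. Section 1.9 reports no clinically significant laboratory abnormalities with the trial regimen. Section 1.5 presents a less toxic alternative to current therapies, NECT included, as a need. Either arm could be the more symptomatic one.

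Section 9.9 also plans confidence intervals for AE incidence and states no safety hypothesis test, so no decision rule hangs on the count.

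**Conclusion.** The inconsistency stands. As written, 6.5.1 can leave a grade 3-4 laboratory result unreported as an AE, although the section 6.5 endpoints say that such results are included, and no other rule restores the grade. The consequence is possible undercounting in the grade ≥ 3 endpoints, both overall and treatment-related. A bias between arms arises only if linkage differs between them. Open-label judgement of association makes that possible, but the protocol does not establish its direction or size. Over the assumed ranges the spurious difference runs from 0 (equal linkage) to 8 points (a 20% true rate, 80% v 40% with an earlier event, all judged linked). The upper end needs extreme assumptions.

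The per-patient any-AE endpoint, the 8.2 discontinuation rules, the ALAT/ASAT-plus-bilirubin serious AE and the 9.9 laboratory tables are not materially affected. Severity: minor.

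**What to change.** 1. In 6.5.1, limit the exemption to avoiding a second AE line for the same episode. State that the combined event takes the higher of its clinical and laboratory grades. Its causality judgement then serves the treatment-related endpoint. Say how this sits with the opening sentence of the section.
2. Count the laboratory component of the grade ≥ 3 endpoint from the recorded, graded laboratory values in both arms, whether or not an AE form exists.
3. Reconcile 6.5.9 with 6.5.1, so that it is clear whether the repeat-test rule covers a result that has no AE entry of its own.

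The cost is a sentence or two in the protocol and some programming on data already collected. Reported grade ≥ 3 rates may come out slightly higher.

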6.5.2. Definition of SAE

An SAE is any AE that:

- results in death,
- is life-threatening,
- requires in-patient hospitalisation or prolongation of existing hospitalisation,
- results in persistent or significant disability/incapacity,
- is a congenital anomaly/birth defect,
- is an important medical event that may not be immediately lifethreatening or result in death or hospitalisation but may jeopardise the patient or may require intervention to prevent one of the other outcomes listed in the definition above.
- In this study, ALAT or ASAT levels more than 3 x ULN associated with a total bilirubin level more than 2 x ULN will be considered as SAEs.

SAEs also include any other events defined in the present protocol or by the regulatory authorities in the country in which the event occurs.

For the purposes of this study, hospitalisation for uncomplicated delivery will not be considered as an SAE.

